6.2.2.5 Biopsy Procedures

Participants will undergo core needle biopsy of normal breast tissue and the entire specimen will be submitted in total to research. The patient will not receive any results of the biopsy. Which breast to sample for biopsy will be at the discretion of the treating physician. This biopsy will not be directed at a particular lesion, but instead will be directed to the upper outer quadrant of the breast, which is typically a dense region of the breast. Core needle biopsy of the breast will be performed using a 14-gauge needle. After providing local anesthesia, a small skin incision is made in the breast and the core needle inserted. Up to four core biopsies are taken through this single incision, and after completing the biopsies, the wound is steri-stripped, dressed, and ice is placed on the wound to minimize bruising and scarring. The participant is encouraged to keep ice on the biopsy site for up to 2 hours. Part of the breast biopsy specimen will be saved as frozen tissue and other part will be placed in fixative for H & E and immunohistochemical staining for biomarkers. Potential complications include bleeding, pain, hematoma formation and bruising, or infection. The first biopsy will be before beginning hydroxytyrosol and the second biopsy will be done after treatment with hydroxytyrosol for one year. There will be no attempt to biopsy the exact same area of the breast or the same on the second breast biopsy. Instead, the upper outer quadrant of the breast will again be sampled.

Breast tissue can be collected from a scheduled biopsy or surgery and used in place of the breast biopsy.

Rationale for Mandatory Biopsy before and after the treatment with hydroxytyrosol.

Identifying risk biomarkers in benign breast tissue may provide direct measure of the effect of treatment on target tissue beyond any information imaging can provide. Ki-67 expression in benign breast tissue has been included into many early phase chemoprevention trials[34,35]. Unfortunately there are many limitations of using Ki67 expression in benign tissue (due to very low baseline Ki67 in these patients) and other tissue biomarkers are necessary. Therefore biopsy including markers for apoptosis, stem cell as well as Wnt Pathway (primary action of hydroxytyrosol) is proposed. Ki-67 expression does not have correlation with mammographic density therefore it is possible for the patient to have tissue changes but not able to detect it in the mammogram[36].

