reported as a follow-up to that event regardless of when it occurs. The follow-up information should describe whether the event has resolved or continues, if and how it was treated, whether the blind was broken or not (if applicable), and whether the patient continued or withdrew from study participation.

If the SAE is not previously documented in the Hydroxytyrosol Investigator Brochure or Package Insert (new occurrence) and is thought to be related to the study drug, may urgently require further information from the investigator for Health Authority reporting. TMHCC and TMHRI may need to issue an Investigator Notification (IN), to inform all investigators involved in any study with the same drug that this SAE has been reported. Suspected Unexpected Serious Adverse Reactions (SUSARs) will be collected and reported to the competent authorities and relevant ethics committees in accordance with Directive 2001/20/EC or as per national regulatory requirements in participating countries.

For Comparator Drugs/Secondary Suspects (Concomitant Medications), all serious adverse experiences will be forwarded to the comparator drug company by the investigator.

9 Statistical methods

Study Design and Sample Size. This is a single-arm, pilot breast cancer prevention study of hydroxytyrosol in women at increased risk of breast cancer. Our primary study endpoint will be defined as proportion of women who exhibit a 10% absolute reduction in mammographic density at one-year of follow-up (Cuzick JNCI 2011). For each of the post and pre-menopausal group of women, we will assume under the null hypothesis that 25% of women will exhibit a response (at least a 25% reduction from baseline) versus an alternative hypothesis equal to 45% based on data presented from Cuzick (JNCI 2011). Under these assumptions, a sample of 50 pre-menopausal and 50 post-menopausal women will provide 85% power based on a two-sided test for a single proportion with 5% significance level for each group of women.

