Statistical Analysis. Demographics and pre-treatment characteristics will be summarized for 50 premenopausal & 50 postmenopausal women using descriptive statistics. Mammographic density levels at baseline and follow-up time-points as well as categorized levels based on BIRAD criteria will also be summarized using means, standard deviations and proportions. Change from baseline levels of breast density will be analyzed using paired tests while the proportion of women who exhibit at least a 10% absolute reduction from baseline will be calculated along with 95% binomial confidence intervals for each group of women.

Correlative endpoints including Ki-67, apoptosis, Wnt signaling and stem cell pathway markers will likewise be summarized descriptively at each time point of follow-up. Correlations between these markers and with mammographic density levels will be assessed using Spearman or Pearson's correlation coefficients. Change from baseline levels will be analyzed using paired t-test or Wilcoxon-signed rank test.

Multivariate analysis to adjust for demographic/clinical characteristics, specifically age or menopausal status (pre, peri, and post) will likewise be considered using logistic regression for analyzing proportion of women with response or using linear regression models for analysis of quantitative levels of mammographic density. Given the pilot nature of this study, these multivariate analyses will be considered exploratory.

Expected outcome: We expect a decrease in apoptosis, cell proliferation, in post-treatment breast tissue in comparison to pre-treatment. Our previous data reveal an inhibition of Wnt signaling by HT, thus we expect a change in this signaling in this prevention study.

Potential pitfalls, and resolutions: If we do not have enough breast tissue for all determinations, it will be difficult to measure mRNA levels. In such a scenario, we can determine the expression of Sfrp proteins only by multiplex nucleic acid *in situ* hybridization technology (RNAscope) in paraffin embedded tissue slides.

CONFIDENTIAL

10 References:

1. Siegel, R., D. Naishadham, and A. Jemal, Cancer statistics, 2012. *CA Cancer J Clin.* 62(1): p. 10-29.
2. Anderson, D.E., Genetic study of breast cancer: identification of a high risk group. *Cancer*, 1974. 34(4): p. 1090-7.
3. Jatoi, I. and A.B. Miller, Why is breast-cancer mortality declining? *Lancet Oncol.* 2003. 4(4): p. 251-4.

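### The planned marker correlations take no account of menopausal group, so an unadjusted coefficient could be inflated or masked if both correlated variables differ between pre- and post-menopausal women

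*Combined protocol and SAP*

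**What the plan says.** Section 9 (Statistical methods) sizes the trial by menopausal group: "a sample of 50 pre-menopausal and 50 post-menopausal women will provide 85% power", using a "two-sided test for a single proportion with 5% significance level for each group of women". The Statistical Analysis text keeps that division for the primary responder proportion, which "will be calculated along with 95% binomial confidence intervals for each group of women".

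The next paragraph covers Ki-67, apoptosis, Wnt and stem-cell markers. It plans descriptive summaries by time point and then: "Correlations between these markers and with mammographic density levels will be assessed using Spearman or Pearson's correlation coefficients". No group, stratum or covariate is named there.

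Menopausal status returns one paragraph later: "Multivariate analysis to adjust for demographic/clinical characteristics, specifically age or menopausal status (pre, peri, and post) will likewise be considered using logistic regression" for response, or linear regression for density levels. These models are labelled exploratory, and no marker is named in them as outcome or predictor. No other section supplies a grouping for the correlations.

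Section 6.2.2.5 (Biopsy Procedures) is also relevant. Its rationale for the mandatory biopsy includes: "Ki-67 expression does not have correlation with mammographic density therefore it is possible for the patient to have tissue changes".

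**The concern.** The design treats pre- and post-menopausal women as two populations, yet the correlation sentence mentions neither. When two groups with different means on both variables enter one coefficient, the distance between the group means adds to the covariance. The coefficient then mixes within-group association with the group difference. It can be positive with no association inside either group, or near zero when a real association runs against the group difference.

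What is at stake is the interpretation of the tissue data. The biopsy rationale relies in part on an absence of correlation between Ki-67 and density, and the planned coefficient is the trial's own look at that relation. If it is computed without regard to group, a reader could not tell whether it supports or contradicts that statement for biological reasons or because of the mix of women enrolled.

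**Working it through.** **1. The plan's own figure.** The only stated power is 85% per group for the primary proportion: "under the null hypothesis that 25% of women will exhibit a response" "versus an alternative hypothesis equal to 45" per cent, n = 50, two-sided 5%.
- Arcsine: 2 × (arcsin√0.45 − arcsin√0.25) × √50 − 1.96 = 0.4234 × 7.071 − 1.96 = 1.034, so power is 84.9%.
- Normal approximation with continuity correction: 84.0%.
- Exact binomial with equal tails (success at 20 or more of 50): 80.3%.

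The 85% is reproduced by the usual approximations. It concerns the primary proportion only. No sample size, significance level or power is given for the correlations.

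**2. Formula for an unadjusted coefficient.** Let p be the share of women in one group and v = p(1 − p). Let d1 and d2 be the pre/post mean differences in within-group SD units, and r_w the within-group correlation. Then

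r = (r_w + v·d1·d2) / √[(1 + v·d1²)(1 + v·d2²)].

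With 50+50 women, v = 0.25. The documents give no values for d1 or d2, so a range is assumed. The chance of p<0.05 uses Fisher's z with √(100 − 3) = 9.849.

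**3. False association (r_w = 0, n = 100).**

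| Shift on each variable (SD) | Expected r | Chance of p<0.05 |
|---|---|---|
| 0.3 and 0.3 | 0.0225/1.0225 = 0.02 | 5.5% |
| 0.5 and 0.5 | 0.0625/1.0625 = 0.06 | 9% |
| 0.8 and 0.5 | 0.10/1.110 = 0.09 | 14% |
| 0.8 and 0.8 | 0.16/1.16 = 0.14 | 28% |
| 1.0 and 1.0 | 0.25/1.25 = 0.20 | 52% (simulation 53%) |
| 0.8 and 0 | 0 | 5% |

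Simulation with 3,000 data sets per setting agrees. Pearson and Spearman behave alike (28% each at 0.8/0.8), so choosing Spearman gives no protection. A group-centred partial correlation on the same data rejects in 4.0% to 5.5%. That adjusted test was of Pearson type; a partial Spearman test was not itself simulated.

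**4. Masking (r_w = −0.30, shifts in the same direction, n = 100).**
- 0.5/0.5: r = (−0.30 + 0.0625)/1.0625 = −0.22; detected in 61%.
- 0.8/0.8: r = (−0.30 + 0.16)/1.16 = −0.12; 22%.
- 1.0/1.0: r = (−0.30 + 0.25)/1.25 = −0.04; 7%.

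The adjusted estimate on all 100 women has atanh(0.30) × √96 − 1.96 = 0.3095 × 9.798 − 1.96 = 1.073, or 86%. A coefficient from one group of 50 has 0.3095 × √47 − 1.96 = 0.162, or 56%.

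**5. Split and number.** The term v is largest at an even split. At 80/20, v = 0.16, and for d = 0.8 on both variables r = 0.1024/1.1024 = 0.09 instead of 0.14. Table 7-1, footnote 9, says women already on study will not be asked to have the mandatory biopsy. The number with tissue may therefore be below 100, and its split is unknown. With 30+30 women, shifts of 0.5, 0.8 and 1.0 SD give p<0.05 in about 7–8%, 18% and 34%.

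**The case against.** The strongest reply is that the plan is silent and does not prescribe pooling. The marker paragraph follows text about the two groups and says the markers are to be summarised likewise, so results by group are a possible reading. That stands: a reader might infer that pooling is planned, and the documents do not say so. They also do not rule it out, and an unqualified coefficient leaves the choice open until the data are seen.

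Second, the bias needs both variables to differ by menopausal status, and the documents show no such difference for any marker. Section 6.2.2.5 describes very low baseline Ki-67, which may leave little room for one. A reader might also take the protocol to say that menopausal status shifts density. The passages on hormonal changes (Section 5.1, criterion 12; Section 6.2.2.8, item c) concern contraceptive switching and pregnancy on study. The firmer support is that Section 9 itself lists menopausal status as an adjustment factor for density. The eligibility floor of more than 10% density also restricts the range. All of this stands and limits the weight of the point.

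Third, the analysis is exploratory and carries no stated test or decision rule, so the chance of p<0.05 is a yardstick here and not a planned error rate. Section 3 lists the markers as exploratory (Section 4.1 calls them secondary), and neither makes marker-density correlation an objective. This also stands.

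Fourth, a reader might extend the point to correlations of changes. The sentence names density levels, and the plan assumes the same response rates in both groups, so nothing in it suggests different density changes by group.

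**Conclusion.** The point holds as a low-cost improvement to an exploratory analysis. Section 9 specifies plain coefficients and does not use the menopausal grouping on which the rest of the design rests; the exploratory regressions do not repair this. If both variables differ by menopausal status, an unadjusted coefficient is biased. Under the assumed even split the bias is negligible at 0.3 SD on each variable, small at 0.5 SD, and material from about 0.8 SD. It shrinks with an uneven split and vanishes if only one variable differs.

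A reader might go further and conclude that the reported associations would reflect the sampling design and not biology. The documents do not support that: they give no group difference for any marker, and the larger error rates rest on assumed shifts of 0.8 SD or more on both variables. The primary endpoint and its power are unaffected.

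**What to change.** Replace the correlation sentence in Section 9 with:

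*Correlations will be estimated as partial Spearman correlations adjusted for menopausal group (pre/post as defined in Section 7.2.2, Determination of Menopausal Status), with the two group-specific coefficients shown descriptively.*

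Naming the definition matters because Section 9 lists pre, peri and post, while Section 7.2.2 defines only pre and post.

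The cost is one degree of freedom for the adjusted estimate (97 instead of 98 at n = 100) and no new data. The group-specific coefficients are less precise, as the 56% against 86% for r = 0.3 shows, so they should accompany the adjusted estimate and not be the main result. The change removes the group difference only. Age, which Section 9 names beside menopausal status, is not adjusted for.

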Appendix A: ECOG Performance Status Criteria

ECOG Performance Status Scale	
Grade	Descriptions
0	Normal activity. Fully active, able to carry on all pre-disease performance without restriction.
1	Symptoms, but ambulatory. Restricted in physically strenuous activity, but ambulatory and able to carry out work of a light or sedentary nature (e.g., light housework, office work).
2	In bed < 50% of the time. Ambulatory and capable of all self-care, but unable to carry out any work activities. Up and about more than 50% of waking hours.
3	In bed > 50% of the time. Capable of only limited self-care, confined to bed or chair more than 50% of waking hours.
4	100% bedridden. Completely disabled. Cannot carry on any self-care. Totally confined to bed or chair.
5	Dead

Appendix B: New York Heart Association (NYHA) Classifications

Class	Description
I	Patients with cardiac disease but without resulting limitations of physical activity. Ordinary physical activity does not cause undue fatigue, palpitation, dyspnea, or anginal pain.
II	Patients with cardiac disease resulting in slight limitation of physical activity. They are comfortable at rest. Ordinary physical activity results in fatigue, palpitation, dyspnea, or anginal pain.
III	Patients with cardiac disease resulting in marked limitation of physical activity. They are comfortable at rest. Less than ordinary physical activity causes fatigue, palpitation, dyspnea, or anginal pain.
IV	Patients with cardiac disease resulting in inability to carry on physical activity without discomfort. Symptoms of cardiac insufficiency or of the anginal syndrome may be present even at rest. If any physical activity is undertaken, discomfort is increased.

This table is an excerpt from the Oxford Textbook of Medicine, 2nd ed. Oxford; New York: Oxford University Press, 1987, p. 2228.

Appendix C: CTCAE Files

Version 4.0 (dated June-14-2010)

NCI Common Terminology Criteria for Adverse Events (CTCAE) v.4 data files and related documents are published here. The most current release files appear in this directory:

Files: Booklet	Content
CTCAE 4.03 2010-06-14 QuickReference 5x7.pdf	Most recent release of core terminology: PDF document, traditional small booklet format.

<http://evs.nci.nih.gov/ftp1/CTCAE/About.html>

CONFIDENTIAL

